### **10.1.5. Dissemination of Clinical Study Data**

- Where required by applicable regulatory requirements, an investigator signatory will be identified for the approval of the clinical study report. The investigator will be provided reasonable access to statistical tables, figures, and relevant reports and will have the opportunity to review the complete study results at a GSK site or other mutually-agreeable location.
- GSK will also provide all investigators who participated in the study with a summary of the study results and will tell the investigators what treatment their patients' received. The investigator(s) is/are encouraged to share the summary results with the study subjects, as appropriate.
- Under the framework of the SHARE initiative, GSK intends to make anonymized participant-level data from this trial available to external researchers for scientific analyses or to conduct further research that can help advance medical science or improve patient care. This helps ensure the data provided by trial participants are used to maximum effect in the creation of knowledge and understanding. Requests for access may be made through [www.clinicalstudydatarequest.com](http://www.clinicalstudydatarequest.com).
- GSK will provide the investigator with the randomization codes for their site only after completion of the full statistical analysis.

### **10.1.6. Data Quality Assurance**

- All participant data relating to the study will be recorded on printed or electronic CRF unless transmitted to the sponsor or designee electronically (e.g., laboratory data). The investigator is responsible for verifying that data entries are accurate and correct by physically or electronically signing the CRF.
- Quality tolerance limits (QTLs) will be pre-defined in the QTL plan to identify systematic issues that can impact participant safety and/or reliability of study results. These pre-defined parameters will be monitored during and at the end of the study and all deviations from the QTLs and remedial actions taken will be summarized in the clinical study report.
- The investigator must permit study-related monitoring, audits, IRB/IEC review, and regulatory agency inspections and provide direct access to source data documents.
- Monitoring details describing strategy including definition of study critical data items and processes (e.g., risk-based initiatives in operations and quality such as Risk Management and Mitigation Strategies and Analytical Risk-Based Monitoring), methods, responsibilities and requirements, including handling of noncompliance issues and monitoring techniques (central, remote, or on-site monitoring) are provided in the Monitoring Plan.
- The sponsor or designee is responsible for the data management of this study including quality checking of the data.
- The sponsor assumes accountability for actions delegated to other individuals (e.g., Contract Research Organizations).

- Records and documents, including signed ICF, pertaining to the conduct of this study must be retained by the investigator for 25 years from the issue of the final CSR/ equivalent summary unless local regulations or institutional policies require a longer retention period. No records may be destroyed during the retention period without the written approval of the sponsor. No records may be transferred to another location or party without written notification to the sponsor.

#### **10.1.7. Source Documents**

- Source documents provide evidence for the existence of the participant and substantiate the integrity of the data collected. Source documents are filed at the investigator's site.
- Data reported on the CRF or entered in the eCRF that are transcribed from source documents must be consistent with the source documents or the discrepancies must be explained. The investigator may need to request previous medical records or transfer records, depending on the study. Also, current medical records must be available.
- Definition of what constitutes source data and its origin can be found in Source Data Agreement.
- The investigator must maintain accurate documentation (source data) that supports the information entered in the CRF.
- Study monitors will perform ongoing source data verification to confirm that data entered into the CRF by authorized site personnel are accurate, complete, and verifiable from source documents; that the safety and rights of participants are being protected; and that the study is being conducted in accordance with the currently approved protocol and any other study agreements, ICH GCP, and all applicable regulatory requirements.

#### **10.1.8. Study and Site Start and Closure**

The study start date is the date on which the clinical study will be open for recruitment of participants.

GSK or designee reserves the right to close the study site or terminate the study at any time for any reason at the sole discretion of GSK. Study sites will be closed upon study completion. A study site is considered closed when all required documents and study supplies have been collected and a study-site closure visit has been performed.

The investigator may initiate study-site closure at any time, provided there is reasonable cause and sufficient notice is given in advance of the intended termination.

Reasons for the early closure of a study site by the sponsor or investigator may include but are not limited to:

For study termination:

- Discontinuation of further study intervention development

For site termination:

- Failure of the investigator to comply with the protocol, the requirements of the IRB/IEC or local health authorities, the sponsor's procedures, or GCP guidelines
- Inadequate or no recruitment of participants (evaluated after a reasonable amount of time) by the investigator
- If the study is prematurely terminated or suspended, the sponsor shall promptly inform the investigators, the IECs/IRBs, the regulatory authorities, and any contract research organization(s) used in the study of the reason for termination or suspension, as specified by the applicable regulatory requirements. The investigator shall promptly inform the subject and should assure appropriate participant therapy and/or follow-up

#### **10.1.9. Publication Policy**

- The results of this study may be published or presented at scientific meetings. If this is foreseen, the investigator agrees to submit all manuscripts or abstracts to the sponsor before submission. This allows the sponsor to protect proprietary information and to provide comments.
- The sponsor will comply with the requirements for publication of study results. In accordance with standard editorial and ethical practice, the sponsor will generally support publication of multicenter studies only in their entirety and not as individual site data. In this case, a coordinating investigator will be designated by mutual agreement.
- Authorship will be determined by mutual agreement and in line with International Committee of Medical Journal Editors authorship requirements.

## 10.2. Appendix 2: Clinical Laboratory Tests

- The tests detailed in [Table 6](#) will be performed by the local laboratory.
- Protocol-specific requirements for inclusion or exclusion of participants are detailed in [Section 5](#) of the protocol.
- Additional tests may be performed at any time during the study as determined necessary by the investigator or required by local regulations.

**Table 6 Protocol-Required Safety Laboratory Tests**

| Laboratory Assessments          | Parameters  |           |  |                            |   |  |  |  |
|---------------------------------|---|-----------|--|----------------------------|---|--|--|--|
| Hematology                      | Platelet Count  |           | RBC Indices:
MCV
MCH
%Reticulocytes                                     |                            | White blood cell (WBC) count with Differential:
Neutrophils
Lymphocytes
Monocytes
Eosinophils
Basophils |  |  |  |
|                                 | Red blood cell (RBC) Count  |           |  |                            |   |  |  |  |
|                                 | Hemoglobin  |           |  |                            |   |  |  |  |
|                                 | Hematocrit  |           |  |                            |   |  |  |  |
| Clinical Chemistry  | BUN   | Potassium | Aspartate Aminotransferase (AST)/ Serum Glutamic-Oxaloacetic Transaminase (SGOT) | Total and direct bilirubin |   |  |  |  |
|                                 | Creatinine  | Sodium    | Alanine Aminotransferase (ALT)/ Serum Glutamic-Pyruvic Transaminase (SGPT)       | Total Protein              |   |  |  |  |
|                                 | Glucose (fasting)   | Calcium   | Alkaline phosphatase   |                            |   |  |  |  |
| Routine Urinalysis              | 
 
• Specific gravity
 
• pH, glucose, protein, blood, ketones, bilirubin, urobilinogen, nitrite, leukocyte esterase by dipstick
 
• Microscopic examination (if blood or protein is abnormal)
 
 |           |  |                            |   |  |  |  |
| Pregnancy testing               | 
 
• Highly sensitive Serum human chorionic gonadotropin (hCG) pregnancy test (as needed for women of childbearing potential)
 
  |           |  |                            |   |  |  |  |
| Other Screening Tests           | 
 
• Follicle-stimulating hormone and estradiol (as needed in women of non-childbearing potential only)
 
  |           |  |                            |   |  |  |  |

| Laboratory Assessments | Parameters   |
|------------------------|--|
|                        | 
 
• Urine alcohol and drug screen (to include at minimum: amphetamines, barbiturates, cocaine, opiates, cannabinoids and benzodiazepines)
 
• Serology (HIV antibody, hepatitis B surface antigen [HBsAg], and hepatitis C virus antibody)
 
• COVID-19 testing (performed at additional time noted in the SoA tables and as required)
 
 |

## NOTES :

1. Details of liver chemistry stopping criteria and required actions and follow-up assessments after liver stopping or monitoring event are given in Section 7.1 and Section 10.5. All events of ALT  $\geq 3 \times$  upper limit of normal (ULN) and total bilirubin  $\geq 2 \times$  ULN ( $> 35\%$  direct bilirubin) or ALT  $\geq 3 \times$  ULN and international normalized ratio (INR)  $> 1.5$ , if INR measured, which may indicate severe liver injury (possible Hy's Law), must be reported to GSK in an expedited manner (excluding studies of hepatic impairment or cirrhosis).
2. If alkaline phosphatase is elevated, consider fractionating.

## 10.3. Appendix 3: AEs and SAEs: Definitions and Procedures for Recording, Evaluating, Follow-up, and Reporting

### 10.3.1. Definition of AE

| AE Definition   |
|---|
| 
 
• An AE is any untoward medical occurrence in a clinical study participant, temporally associated with the use of a study intervention, whether or not considered related to the study intervention.
 
• NOTE: An AE can therefore be any unfavorable and unintended sign (including an abnormal laboratory finding), symptom, or disease (new or exacerbated) temporally associated with the use of a study intervention.
 
 |

| Events Meeting the AE Definition  |
|--|
| 
 
• Any abnormal laboratory test results (hematology, clinical chemistry, or urinalysis) or other safety assessments (e.g., ECG, radiological scans, vital signs measurements), including those that worsen from baseline, considered clinically significant in the medical and scientific judgment of the investigator (i.e., not related to progression of underlying disease).
 
• Exacerbation of a chronic or intermittent pre-existing condition including either an increase in frequency and/or intensity of the condition.
 
• New conditions detected or diagnosed after study intervention administration even though it may have been present before the start of the study.
 
• Signs, symptoms, or the clinical sequelae of a suspected drug- drug interaction.
 
• Signs, symptoms, or the clinical sequelae of a suspected overdose of either study intervention or a concomitant medication. Overdose per se will not be reported as an AE/SAE unless it is an intentional overdose taken with possible suicidal/self-harming intent. Such overdoses should be reported regardless of sequelae.
 
 |

| Events NOT Meeting the AE Definition   |
|---|
| 
 
• Any clinically significant abnormal laboratory findings or other abnormal safety assessments which are associated with the underlying disease, unless judged by the investigator to be more severe than expected for the participant's condition.
 
• Medical or surgical procedure (e.g., endoscopy, appendectomy): the condition that leads to the procedure is the AE.
 
• Situations in which an untoward medical occurrence did not occur (social and/or convenience admission to a hospital).
 
 |

- Anticipated day-to-day fluctuations of pre-existing disease(s) or condition(s) present or detected at the start of the study that do not worsen.

### 10.3.2. Definition of SAE

|  |   |
|--|---|
| An SAE is defined as any serious adverse event that, at any dose:                 |   |
| a. Results in death   |   |
| b. Is life-threatening  | 
The term 'life-threatening' in the definition of 'serious' refers to an event in which the participant was at risk of death at the time of the event. It does not refer to an event, which hypothetically might have caused death, if it were more severe.
   |
| c. Requires inpatient hospitalization or prolongation of existing hospitalization | 
 
• In general, hospitalization signifies that the participant has been admitted (usually involving at least an overnight stay) at the hospital or emergency ward for observation and/or treatment that would not have been appropriate in the physician's office or outpatient setting. Complications that occur during hospitalization are AE. If a complication prolongs hospitalization or fulfils any other serious criteria, the event is serious. When in doubt as to whether "hospitalization" occurred or was necessary, the AE should be considered serious.
 
• Hospitalization for elective treatment of a pre-existing condition that did not worsen from baseline is not considered an AE.
 
 |
| d. Results in persistent or significant disability/incapacity                     | 
 
• The term disability means a substantial disruption of a person's ability to conduct normal life functions.
 
• This definition is not intended to include experiences of relatively minor medical significance such as uncomplicated headache, nausea, vomiting, diarrhea, influenza, and accidental trauma (e.g. sprained ankle) which may interfere with or prevent everyday life functions but do not constitute a substantial disruption.
 
  |
| e. Is a congenital anomaly/birth defect   |   |
| f. Other situations:  | 
 
• Possible Hy's Law case: ALT<math>\geq</math>3xULN AND total bilirubin <math>\geq</math>2xULN (<math>>35\%</math> direct bilirubin) or international normalized ratio (INR) <math>>1.5</math> must be reported as SAE
 
• Medical or scientific judgment should be exercised by the investigator in deciding whether SAE reporting is appropriate in other situations such as significant medical events that may jeopardize the participant or may require
 
   |

medical or surgical intervention to prevent one of the other outcomes listed in the above definition. These events should usually be considered serious.

- Examples of such events include invasive or malignant cancers, intensive treatment for allergic bronchospasm, blood dyscrasias, convulsions, or development of intervention dependency or intervention abuse.

### 10.3.3. Definition of Cardiovascular Events

#### Cardiovascular Events (CV) Definition:

Investigators will be required to fill out the specific CV event page of the CRF for the following AEs and SAEs:

- Myocardial infarction/unstable angina
- Congestive heart failure
- Arrhythmias
- Valvulopathy
- Pulmonary hypertension
- Cerebrovascular events/stroke and transient ischemic attack
- Peripheral arterial thromboembolism
- Deep venous thrombosis/pulmonary embolism
- Revascularization

### 10.3.4. Recording and Follow-Up of AE and SAE

#### AE and SAE Recording

- When an AE/SAE occurs, it is the responsibility of the investigator to review all documentation (e.g. hospital progress notes, laboratory, and diagnostics reports) related to the event.
- The investigator will then record all relevant AE/SAE information.
- It is **not** acceptable for the investigator to send photocopies of the participant's medical records to GSK in lieu of completion of the GSK required form.
- There may be instances when copies of medical records for certain cases are requested by GSK. In this case, all participant identifiers, with the exception of the participant number, will be redacted on the copies of the medical records before submission to GSK.

- The investigator will attempt to establish a diagnosis of the event based on signs, symptoms, and/or other clinical information. Whenever possible, the diagnosis (not the individual signs/symptoms) will be documented as the AE/SAE.

### Assessment of Intensity

The investigator will make an assessment of intensity for each AE and SAE reported during the study and assign it to 1 of the following categories:

- Mild: An event that is easily tolerated by the participant, causing minimal discomfort and not interfering with everyday activities.
- Moderate: An event that causes sufficient discomfort and interferes with normal everyday activities.
- Severe: An event that prevents normal everyday activities. An AE that is assessed as severe should not be confused with an SAE. Severe is a category utilized for rating the intensity of an event; and both AE and SAE can be assessed as severe.
- An event is defined as 'serious' when it meets at least 1 of the predefined outcomes as described in the definition of an SAE, NOT when it is rated as severe.

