### **7.1.2. QTc Stopping Criteria**

A subject that meets either bulleted criterion below will be withdrawn from the study.

- QTcF >500 msec,
- Change from baseline in healthy volunteer participants: QTcF >60 msec

The QTcF correction formula must be used for each participant to determine eligibility for and discontinuation from the study. This formula may not be changed or substituted once the participant has been enrolled. If an ECG demonstrates a prolonged QT interval, two more ECGs should be obtained over 5-10 mins and the average QTcF value of the three ECGs should be used to determine if the participant meets the QTc stopping criteria see Section 8.2.3.

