### **7.1.3. Vital signs Stopping Criteria**

A subject will be withdrawn if any of the following cardiovascular changes are detected up to 24 h post last dose in each session.

- Clinically significant and sustained (i.e., for greater than 2 hours) increase in systolic or diastolic blood pressure, for example:
  - - systolic blood pressure >160 mmHg or >30 mmHg increase from baseline or,
  - - diastolic blood pressure >100 mmHg or >20 mmHg increase from baseline
- Clinically significant and sustained increase in resting heart rate (for example, >120 beats/minute for more than 2 hours)

Withdrawal is to be based on an average value from triplicate blood pressure or heart rate readings. If any blood pressure or heart rate readings are flagged as clinically significant, they are to be repeated in triplicate and checked every 20 minutes until they are no longer clinically significant.

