## **7.2. Study Stopping Criteria.**

### **7.2.1. Safety Stopping Criteria**

In the event of any of the following, ongoing dosing will be halted.

- Two or more participants in the same dose group/cohort experience non-serious severe adverse events considered at least possibly related to the administration of GSK3915393.
- Any participant experiences a serious adverse event considered at least possibly related to the administration of GSK3915393.

The dosing will be temporarily halted, and no further participants will be dosed until a full safety review of the study has taken place. Relevant reporting and discussion with the GSK medical monitor, relevant GSK personnel, and with the CA and IRB / IEC will then take place prior to any resumption of dosing, which may also include the evaluation of lower doses. If following an internal safety review, it is appropriate to restart the trial, a substantial amendment will be submitted to the MHRA and REC. The trial will not restart until the amendment has been approved by the MHRA and REC.

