## 10.5. Appendix 5: Liver Safety: Required Actions and Follow-up Assessments

### Phase I liver chemistry stopping criteria and required follow up assessments

| Liver Chemistry Stopping Criteria  |   |
|--|---|
| Required Actions and Follow up Assessments   |   |
| Actions  | Follow Up Assessments   |
| 
ALT-absolute
 
ALT<math>\geq</math>3xULN
 
If ALT<math>\geq</math>3xULN AND bilirubin <math>\geq</math>2xULN (>35% direct bilirubin) or INR >1.5, Report as an SAE.
 
See additional Actions and Follow Up Assessments listed below
 | 
 
• Immediately discontinue study treatment
 
• Report the event to GSK within 24 hours
 
• Complete the liver event CRF, and complete an SAE data collection tool if the event also meets the criteria for an SAE
 
• Perform liver event follow up assessments
 
• Monitor the subject until liver chemistries resolve, stabilise, or return to within baseline (see MONITORING below)
 
 
MONITORING:
 
If ALT<math>\geq</math>3xULN AND bilirubin <math>\geq</math>2xULN or INR >1.5
 
 
• Repeat liver chemistries (include ALT, AST, alkaline phosphatase, bilirubin) and perform liver event follow up assessments within 24 hrs
 
• Monitor participants twice weekly until liver chemistries resolve, stabilise or return to within baseline
 
• A specialist or hepatology consultation is recommended
 
 
If ALT<math>\geq</math>3xULN AND bilirubin < 2xULN and INR <math>\leq</math>1.5:
 
 
• Repeat liver chemistries (include ALT, AST, alkaline phosphatase, bilirubin) and
 
 |

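### Part B: two symptom-free, non-serious liver stops in one cohort would trigger no mandatory group pause in the protocol text

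*Protocol*

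**What the plan says.** Four parts of the protocol bear on this.

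- **What counts as an AE (10.3.1).** A laboratory abnormality that the investigator judges clinically significant is an AE, so it has to be graded for intensity.
- **How intensity is graded (10.3.4).** All three grades rest on tolerability, discomfort and everyday function. The top grade reads "Severe: An event that prevents normal everyday activities". No grade refers to a laboratory value.
- **When the group stops (7.2.1).** One trigger is a single related serious event. The other is: "Two or more participants in the same dose group/cohort experience non-serious severe adverse events considered at least possibly related to the administration of GSK3915393". After such a halt, a restart needs a substantial amendment: "The trial will not restart until the amendment has been approved by the MHRA and REC".
- **What a liver stop does (7.1.1 and Appendix 5, 10.5).** At ALT of 3 times ULN or more the instruction is "Immediately discontinue study treatment", applied to that participant, with a report to the sponsor within 24 hours. The event is an SAE by rule only if bilirubin reaches 2 times ULN (more than 35% direct) or INR exceeds 1.5. Otherwise the site is told to "complete an SAE data collection tool if the event also meets the criteria for an SAE". Appendix 5 also sets a separate monitoring schedule for raised ALT without those additions, so the protocol expects such cases.

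The SAP adds no stopping rule. It refers the details of dose escalation and its data review to the dose escalation plan.

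**The concern.** The group rule counts events by how the participant feels and functions. The individual liver rule works on a laboratory value that may be raised with no symptoms at all. The two do not meet: a participant can be taken off drug for a liver signal that counts as zero toward the cohort halt.

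Part B is where this matters. Dosing is twice daily for 14 days, with 9 active and 3 placebo participants per cohort. Idiosyncratic hepatotoxicity is the first risk listed in 2.3.1. Section 4.3.4 says that risk is much lower below 100 mg/day. The example doses in 4.3.7 of 20, 60 and 160 mg BID are 40, 120 and 320 mg/day, so two of the three exceed that level. At stake is whether the rest of a cohort goes on being dosed after two like liver signals with no required review.

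**Working it through.** **Rule logic.** Take one Part B participant with ALT of at least 3 times ULN, no symptoms, normal bilirubin and INR, judged related.

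1. The finding is an AE if clinically significant (10.3.1).
2. It does not interfere with activity, so the literal grade is mild (10.3.4).
3. It is not an SAE by the liver rule (10.3.2, 10.5).
4. The participant stops (7.1.1, 10.5).
5. Its contribution to the severe-event count in 7.2.1 is 0, and to the SAE trigger 0.

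Two such participants contribute 0 + 0. Section 7.2.2 does not help: it depends on exposure and stops escalation only. On a literal reading, the chance of a mandatory halt from these findings is therefore 0 at any event rate.

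**The plan's own figures.** It gives none for the stopping rule. The nearest are the exact 95% upper limits for 9 active participants in Protocol 9.2. They reproduce:

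- 0/9: 1 − 0.025^(1/9) = 0.336, stated as 33.6%.
- 1/9: the 97.5% beta quantile with parameters 2 and 8 = 0.4825, stated as 48.2%.

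These are limits on what 9 participants can exclude, not expected liver event rates.

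**How often two or more would occur.** The per-participant rate p is an assumption. With n at risk, P(at least 2) = 1 − (1 − p)^n − n·p·(1 − p)^(n−1). For n = 9 and p = 0.05: 1 − 0.6302 − 0.2985 = 0.071.

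| Assumed rate p | Events on active only, n = 9 | Events in anyone, n = 12 |
|---|---|---|
| 1% | 0.3% | 0.6% |
| 2% | 1.3% | 2.3% |
| 5% | 7.1% | 11.8% |

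**Upper bound on what the gap could cost.** The sentinel pair (1 active, 1 placebo) runs at least 4 days ahead, leaving 8 active and 2 placebo in the main group. Suppose 2 of the 8 meet the criterion at the same scheduled sample, results are back before the next day's dose, and nobody acts on the two 24-hour reports. The other 6 active participants could then receive 6 × 2 × (14 − sample day) further doses in total:

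- Day 3 sample: 6 × 2 × 11 = 132
- Day 7 sample: 6 × 2 × 7 = 84
- Day 11 sample: 6 × 2 × 3 = 36

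This is a ceiling under inaction, not a forecast.

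**The case against.** The strongest reply is that the protocol leaves ample room to act.

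- Under 10.3.2 the investigator may class a significant medical event as serious, with the steer "These events should usually be considered serious", and one related SAE halts dosing.
- INR is obtained and rechecked after an ALT stop, so a worsening case moves toward the SAE rule.
- Section 7.1.1 also requires stopping for lesser liver changes when the investigator thinks it best for that participant.
- The sponsor hears within 24 hours, the Medical Monitor is available, sentinels go first, and escalation waits for 14 days of safety data.
- Appendix 1 allows changes without prior approval to remove an immediate hazard, and lets the sponsor end the study.

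All of this stands, and it is why the point is modest. None of it closes the gap. Each route is a matter of judgment, concerns one participant, applies only once bilirubin or INR has worsened, or comes after the cohort has finished dosing. For severe symptomatic events the protocol did not rely on judgment; it set a count of two.

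A second reply is that the rule may sit in the Dose Escalation Plan, the DEC charter or the 7.1.1 algorithm figure. None could be checked. The claim is therefore about the protocol text, not the whole safety system.

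A reader might infer two stronger points that the documents do not support.

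- **That the same clause is needed for QTcF and vital signs.** Those rules also act on the individual ("A subject that meets either bulleted criterion below will be withdrawn from the study"; "A subject will be withdrawn if any of the following cardiovascular changes are detected up to 24 h post last dose in each session"). But a confirmed QTcF above 500 msec or marked sustained hypertension may well be called serious and halt dosing that way. The 7.1.3 limits are offered as examples, so counting them would invite dispute. The liver criterion is the clear case.
- **That clusters are likely.** At assumed rates of 10% or 20% the chance of two or more among 9 is 23% or 56%, but nothing in the documents supports such rates. Section 2.3.1 calls the event rare, rates the risk low for short treatment, and reports no adverse liver effects in the 4-week rat and dog studies.

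**Conclusion.** The point holds for Part B and for the liver criterion. On a literal reading of 10.3.4, two or more related, symptom-free ALT stops in one cohort lead to no mandatory group pause anywhere in the protocol text. The chance of that situation is small at low assumed rates: 0.3% to 1.3% per cohort at 1% to 2%, and 7% at 5%, if only active participants can have events. It is 0.6% to 2.3%, and 12%, if all 12 can. These figures assume independent participants with a common rate.

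A reader might infer that the plan is wrong or that the cohort is unprotected. Neither follows: individual stopping is firm, several discretionary safeguards exist, and an investigator might in practice grade or classify a high ALT more severely than the wording requires. Part A is outside the point, because its oral doses are single and a safety review precedes each new oral dose level.

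This is a worthwhile, inexpensive improvement, held with medium confidence because three relevant items were not available.

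**What to change.** Add to section 7.2, separate from the 7.2.1 halt:

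> *In Part B, if two or more participants in the same cohort meet the liver chemistry stopping criterion (7.1.1/10.5) and the events are judged at least possibly related to study intervention, further dosing in that cohort is paused pending a documented safety review by the Medical Monitor and DEC. If the review finds that a 7.2.1 criterion is met, the 7.2.1 halt and restart route applies.*

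Leave QTcF, vital signs and the 10.3.4 grades unchanged. State that the ban on restart in 7.1.4 applies to the participants who met the criterion, so that it is not read as barring the others from resuming. If the Dose Escalation Plan or DEC charter already holds such a rule, a cross-reference is enough.

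The costs are these.

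- **Pauses.** They would occur at the rates in the table if every event is judged related. Placebo events can trigger one, but 6.5 lets the sponsor's Medical Monitor see unblinded data, so it can be reviewed without unblinding the site.
- **Data.** A pause could disturb the Day 3, 5 and 7 food-effect profiles, the Day 14 PK profile and the Day 14 4β-hydroxycholesterol comparison.
- **Process.** A protocol amendment is needed, with ethics approval and, if substantial, health-authority approval. It should make explicit that lifting this lighter pause does not follow the 7.2.1 restart route. It can affect only cohorts not yet dosed; the separate sampling schedule for cohort 1 in the SAP suggests that cohort may already have been under way.

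No new samples, tests or thresholds are required.
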